12.5	Movement Specific Reinvestment Scale.....	29

1 Study Synopsis

Title	A pilot cluster randomised controlled trial, of an implicit learning approach (ILA) versus standard care, on recovery of mobility following stroke.
Protocol Short Title/Acronym	Implicit Learning in Stroke Study (IMPS)
Protocol Version Number and Date	V2 24/09/2018
Study Phase	Pilot (with embedded feasibility)
Study Hypothesis	None
Study Duration	24 months
Methodology	Cluster (Stroke Unit) randomised controlled pilot trial, with nested qualitative exploration of participant and therapist views.
Sponsor Name	Royal Bournemouth and Christchurch Hospitals NHS Foundation Trust and University of Southampton
Chief Investigator	[name]
REC Number	[to be added]
Medical condition under investigation	Stroke
Primary Objective	To establish the feasibility of delivering an ILA during acute stroke rehabilitation (fidelity), and to test the integrity of the study protocol (pilot).
Secondary Objective(s)	To generate data to inform the design of a Phase III trial – including: 
 • Identification of training requirements of clinical teams delivering ILA • Identification of most appropriate outcome measure • Estimation of expected rates of recruitment and retention • Estimation of effect size to enable future sample size calculation • Therapist and patient perceptions of the approach
Number of Clusters	6-8
Number of Participants	60
End Point	3 months post stroke
Main Inclusion Criteria	Clinical diagnosis of stroke; presenting with hemiplegia Within 14 days of stroke onset Medically stable Able to 
 • tolerate daily therapy for a minimum of 30 minutes per session • sit for more than 5 seconds without support • understand and follow 1 stage commands
Primary Outcome Measure	Change in modified Rivermead Mobility Index score at 4 weeks.
Statistical Methodology and Analysis	Within group change scores for all outcome measures with 95% confidence interval

2 Abbreviations

AI	Adverse Incident
HASU	Hyperacute Stroke Unit
ILA	Implicit Learning Approach
FM-LL	Fugl Meyer Assessment – Lower Limb Section
MDT	Multidisciplinary Team
mRMI	Modified Rivermead Mobility Index
MSRS	Movement Specific Reinvestment Scale
SU	Stroke Unit
SwePASS	Modified (Swedish) Postural Adjustment in Stroke Scale

3 Background and Rationale

Around 80% of stroke survivors present with a motor impairment, which affects the control of movement on one side of the body [1]. Much of the focus of rehabilitation, and in particular the work of physiotherapists and occupational therapists, is the recovery of this impaired movement and the associated functions. Yet specific evidence relating to the components of practice that are most effective in promoting motor recovery following stroke is limited.

Regaining the ability to stand, step and walk are important goals for people who have experienced a stroke, and are a common focus during early rehabilitation. Given that one of the key criteria for early discharge from inpatient stroke care is the ability to transfer from bed to chair (+/- assistance) [3], interventions that facilitate the achievement of mobility goals more quickly are also key to reducing length of stay in hospital.

This process of functional recovery post-stroke is underpinned by theories of motor learning, of which there are two broad categories – explicit and implicit. Explicit learning occurs when someone is thinking about what to do, and about how to move – it is a conscious form of learning. Implicit learning occurs through trial and error, and without thinking specifically about how to move – it is a sub-conscious form of learning. There is, already, agreement that two practice conditions are particularly important when differentiating explicit from implicit learning. These are:

- a) the **quantity** of instructions/feedback that therapists give, and
- b) the **focus of attention** derived from these instructions/feedback [4].

Experts consider that high quantity of information and/or promotion of an internal focus of attention (i.e. focussing on body movements) are synonymous with an explicit learning model, and that reduced quantity of information and/or an external focus of attention (i.e. focussing on the environment) are synonymous an implicit learning model [4]. Bias toward one or the other form of learning can therefore be mediated by what the therapist says to a patient.

Implicit and explicit approaches have been well investigated with healthy participants. Research has shown that tasks learnt explicitly are less robust and are less likely to be retained over time, than those learnt implicitly [see 9]. Equally, research in sport has consistently shown that giving excessive verbal information during task practice reduces movement automaticity [5, 6]; and that reduced frequency feedback during task practice can enhance learning [7, 8]. There is strong evidence that people master skills more effectively if they are prompted to focus their attention toward the environment, rather than on their body [see 9 for a review]. Based on current evidence relating to motor learning in stroke, we hypothesise that the ILA will be more effective than standard care (and at a minimum, will be equivalent). There is no evidence, theoretical or empirical, to suggest that utilising an ILA will be detrimental to recovery.

The body of evidence favouring implicit learning is persuasive, and should lead us to challenge current rehabilitation practice, which is **known to be highly explicit in nature** [1, 10, 11]. However, the reported studies typically involve healthy young adults performing sporting activities. Direct transferability to stroke rehabilitation, which is invariably more complex, requires evaluation.

4 Trial Details

This trial will compare an Implicit Learning Approach (ILA) to usual care, during the rehabilitation of mobility post stroke. It is a pilot trial, with embedded feasibility and qualitative evaluations.

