4.13 Proposed Sample Size

Our sample size calculation is based on estimated rates of recruitment and retention. We are aiming to recruit 60 participants in total, across the 6-8 clusters. Each cluster will therefore be required to recruit 7-10 participants.

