4.16 Analysis

Data will be stored and managed using SPSS. Statistical support will be provided by the University of Southampton. Double data entry will be used for paper-based assessments.

The unit of analysis is the individual patient. As this is a pilot study, analysis will primarily be descriptive. Descriptive methods will be used to estimate feasibility of factors relating to the protocol, such as recruitment (proportion of eligible people who consent to the study) and retention (completion of outcome measures at 4 weeks).

Fidelity of the interventions will be established by comparing the number and type of coaching statements delivered to each group. We will describe the mean number of coaching statements per person (and the breakdown of these statements as externally- or internally-focussed) in each group. While we expect large differences, we will not formally test the difference as the study is not designed to do so; we will instead provide an estimate of the difference with corresponding 95% confidence interval. Differences in outcome and potential effect size for the Fugl Meyer, SwePASS and mRMI will be calculated using confidence interval estimation.

5 Process Evaluation

To enable us to understand patient and therapist perceptions and experiences of the ILA, will we be inviting a sub-set of participants to take part in a qualitative evaluation of the ILA.

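### The pilot's effect estimate is meant to inform the Phase III sample size, but 60 patients in 6-8 clusters estimate it too imprecisely, and no other basis for sizing is named

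*Combined protocol and SAP*

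**What the plan says.** The synopsis gives, among the secondary objectives that serve the design of Phase III, "Estimation of effect size to enable future sample size calculation". Estimating recruitment and retention is listed alongside it. The primary outcome is "Change in modified Rivermead Mobility Index score at 4 weeks".

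Section 4.16 carries the objective out: "Differences in outcome and potential effect size for the Fugl Meyer, SwePASS and mRMI will be calculated using confidence interval estimation". It describes the analysis as mainly descriptive and states "The unit of analysis is the individual patient". It mentions no allowance for clustering.

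Section 4.13 sets the size: "We are aiming to recruit 60 participants in total, across the 6-8 clusters", and "Each cluster will therefore be required to recruit 7-10 participants". The basis is given as "Our sample size calculation is based on estimated rates of recruitment and retention", so precision of the effect played no part.

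The documents give no SD, ICC, worthwhile difference or expected interval width. They do not say how the pilot estimate or its interval will be turned into a Phase III sample size.

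**The concern.** A required sample size varies with one over the square of the assumed effect, so an effect estimate that is out by a factor of two makes the sample size wrong by a factor of four. A pilot sized for recruitment and retention, randomised by stroke unit, gives a wide interval for any between-arm effect. If that estimate is the only named input to the Phase III calculation, a chance-high value leads to a trial that is much too small. A chance-low value leads to one much larger than needed, and a value at or below zero gives no sample size at all.

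The quantities such a pilot can estimate tolerably well are the SD, the correlation with baseline and retention. Of these, only retention is named.

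**Working it through.** **The plan's own figure.** The 60 cannot be recomputed, because the recruitment and retention rates behind it are not given. Only the division can be checked: 60/8 = 7.5 and 60/6 = 10, which agrees with 7-10 per cluster up to rounding (8 × 7 = 56).

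**Inputs.** From the documents: N = 60; k = 6 or 8 clusters; mean cluster size m = 10 or 7.5; 95% confidence. Assumed, because the documents give no values: equal clusters split 1:1, no loss to follow-up, ICC 0 to 0.10, true effect 0.3, 0.5 or 0.8 SD. All effects are in SD units of the analysed outcome.

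**Step 1: precision.** SE = √(4 × DE / 60), with DE = 1 + (m − 1) × ICC.

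- ICC 0: DE = 1, SE = √(4/60) = 0.258.
- ICC 0.01: DE = 1.065 (8 clusters) or 1.09 (6), SE = 0.27.
- ICC 0.05: DE = 1.325 or 1.45, SE = 0.297 or 0.311.
- ICC 0.10: DE = 1.65 or 1.90, SE = 0.332 or 0.356.

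The 95% half-width is 1.96 × 0.258 = 0.51 SD at best. With t on k − 2 degrees of freedom it runs from 2.447 × 0.258 = 0.63 (8 clusters, ICC 0) to 2.776 × 0.356 = 0.99 (6 clusters, ICC 0.10). With 20% loss (48 analysed) and no clustering it is 1.96 × √(4/48) = 0.57.

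**Step 2: chance of a fourfold error.** Phase III n is proportional to 1/d². It is at least four times too large when the estimate is at or below d/2 (an estimate at or below zero gives no usable n and is counted here). It is at least four times too small when the estimate is at or above 2d. The probability is Φ(−d/(2 SE)) + Φ(−d/SE).

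| True effect d | SE 0.258 (ICC 0) | SE 0.356 (ICC 0.10, 6 clusters) |
|---|---|---|
| 0.3 | 0.281 + 0.123 = 40% | 0.337 + 0.200 = 54% |
| 0.5 | 0.166 + 0.026 = 19% | 0.241 + 0.080 = 32% |
| 0.8 | 0.061 + 0.001 = 6% | 0.130 + 0.012 = 14% |

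The second term in each cell is the undersizing error. By symmetry it is also the probability of an estimate at or below zero.

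**Step 3: an example.** Take 6 clusters, ICC 0.05 and a true effect of 0.5 SD. The estimate has a 95% range of 0.5 ± 1.96 × 0.311, or −0.11 to 1.11. At 80% power and two-sided 5% (assumed), n per arm = 2(1.96 + 0.8416)²/d², before any Phase III design effect. The true effect needs 63 per arm. The upper end of the range would give 13, and the lower end gives no sample size.

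**Step 4: the alternative.** If the target difference is fixed beforehand and the pilot supplies the SD, Phase III N is proportional to the variance. The 95% limits for the variance on 58 df are 58/80.94 = 0.72 and 58/38.84 = 1.49 times the estimate. With 20% loss (46 df) they are 0.69 and 1.58. These figures ignore clustering.

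**Step 5: can the pilot supply the ICC as well?** At an estimated ICC of 0.05, F = (1 + (m − 1) × 0.05)/0.95, and the upper limit is (F_U − 1)/(F_U + m − 1), where F_U is F times the 97.5% point of the F distribution on (60 − k, k − 2) df.

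- 6 clusters: F = 1.526, F_U = 1.526 × 8.37 = 12.8, upper limit 11.8/21.8 = 0.54.
- 8 clusters: F = 1.395, F_U = 1.395 × 4.975 = 6.94, upper limit 5.94/13.44 = 0.44.

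The lower limit is below zero in both cases and is cut at 0. The pilot ICC is therefore too imprecise to be a main input.

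**The case against.** The best defence is that the plan is modest. Section 4.16 calls the analysis mainly descriptive and specifies intervals, and the synopsis says only that the estimate will enable a calculation. Nothing says that the point estimate will be entered into a formula. That is correct, and the point here is conditional on it. But an interval does not say which value to use, and no alternative input is named. An interval computed on patients without allowing for clustering would also be too narrow whenever the ICC exceeds zero.

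A second defence is that the size of the problem rests on values from outside the documents. That is so. The risk falls as the true effect grows, and the undersizing error alone is 12-20% at 0.3 SD, 3-8% at 0.5 and about 1% or less at 0.8. It does not, however, depend on the assumed ICC, since the lower figure in each range is for no clustering and full retention.

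Three stronger readings are tempting, and the documents do not support them:

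- A reader might infer that the Phase III scale will be chosen by its observed effect, which would add upward selection. The synopsis plans to identify the most suitable outcome measure but states no criterion, and it already names mRMI change as primary.
- A reader might infer that a low or negative estimate would end the programme. No progression rule tied to the effect appears anywhere.
- A reader might infer that retention is overlooked. It is a listed objective, and section 4.16 defines it.

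It is also fair to say that asking this pilot for an ICC would repeat the fault, as step 5 shows. The fix allows for that.

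**Conclusion.** The concern holds in conditional form. The effect-size objective is current text, no other basis for sizing Phase III is named, and the design cannot estimate a between-arm effect closer than about ±0.51 SD. Sizing Phase III on the observed effect would give a sample size wrong by a factor of four or more with probability about 40-54% at a true effect of 0.3 SD, 19-32% at 0.5 and 6-14% at 0.8.

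These figures assume equal clusters, 1:1 allocation, full retention, a normal sampling distribution and ICC 0 to 0.10. Loss to follow-up would make them worse. So would unequal allocation: section 5.2 implies four intervention sites, which with six clusters would be 4:2.

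The pilot's feasibility aims are not affected. The weakness lies in what the pilot passes on to Phase III.

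**What to change.** Reword the synopsis objective along these lines: *Estimation of the SD of 4-week mRMI, its correlation with baseline, and retention (each with 95% CI) to inform the future sample size.*

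Add to section 4.16:

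- The Phase III target difference will be a worthwhile mRMI difference set independently of the pilot estimate.
- The pilot difference will be reported with an interval that allows for clustering. It is descriptive and serves only to check that the target difference is plausible.
- The pilot ICC will be reported with its interval, but the Phase III ICC will come mainly from external sources.

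This needs no extra patients or assessments, only wording and some additional output from data already being collected. The real cost is that the sponsor must justify a worthwhile mRMI difference and find external ICC values.

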4.12 Measures

Measures will be performed and recorded by the stroke research practitioner(s), or designated clinician, at each site. As the research practitioner will not be blind to the intervention arm, all measures will be video recorded, and later scored by a blinded second assessor. Frequent measures are required to understand *rate* of change. Outcome measures have been selected with consideration of international recommendations for measurement of sensorimotor recovery in stroke [12].

At baseline:

- Movement Specific Reinvestment Scale (Self-Report Questionnaire) (MSRS)

At baseline, week 2, week 4, week 6 post enrolment (or up to the point of discharge):

- Fugl Meyer – motor leg sub section
- Modified Postural Adjustment in Stroke Scale (SwePASS)
- Modified Rivermead Mobility Index (mRMI)
- Able to sit for 1 minute unsupported?
- Able to transfer from bed to chair independently?
- Able to walk 10m independently?

At point of discharge

- Discharge destination and care requirements immediately on discharge (number of care visits per day multiplied by the number of carers required)
- Fugl Meyer – motor leg sub section
- Modified Postural Adjustment in Stroke Scale (SwePASS)
- Modified Rivermead Mobility Index (mRMI)
- Able to sit for 1 minute unsupported?
- Able to transfer from bed to chair independently?
- Able to walk 10m independently?
- Movement Specific Reinvestment Scale (MSRS)

At 3 months post enrolment:

- Fugl Meyer – motor leg sub section
- Modified Postural Adjustment in Stroke Scale (SwePASS)
- Modified Rivermead Mobility Index (mRMI)
- Able to sit for 1 minute unsupported?
- Able to transfer from bed to chair independently?
- Able to walk 10m independently?
- Modified Rankin Scale (mRS)
- EQ-5D
- Movement Specific Reinvestment Scale (MSRS)

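### The synopsis lists only within-group change, and the between-arm difference planned in 4.16 is not adjusted for the baseline mRMI, Fugl Meyer and SwePASS scores already collected

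*Combined protocol and SAP*

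**What the plan says.** The statistical row of the synopsis (section 1) contains one entry: "Within group change scores for all outcome measures with 95% confidence interval". The same synopsis sets the primary outcome as "Change in modified Rivermead Mobility Index score at 4 weeks" and lists among the secondary objectives "Estimation of effect size to enable future sample size calculation".

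Section 4.16 sets the tone with "As this is a pilot study, analysis will primarily be descriptive" and then goes further than the synopsis: "Differences in outcome and potential effect size for the Fugl Meyer, SwePASS and mRMI will be calculated using confidence interval estimation". It does not say which time point is meant for Fugl Meyer and SwePASS, and for none of the three scales does it name a model or covariates. For coaching statements the same section is more explicit: "we will instead provide an estimate of the difference with corresponding 95% confidence interval".

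Section 4.12 schedules the three scales, and the sit, transfer and walk items, "At baseline, week 2, week 4, week 6 post enrolment (or up to the point of discharge", and again at discharge and 3 months. The mRS and EQ-5D appear only in the 3-month list. Discharge destination and care requirements appear only at discharge.

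**The concern.** Change within one arm mixes natural recovery after stroke with any effect of treatment. It cannot give the contrast that a Phase III sample size needs. A reader who works from the synopsis alone would therefore not produce the estimate that the secondary objective asks for, and would look for baselines that do not exist for mRS, EQ-5D and discharge status.

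A reader who works from 4.16 would produce a difference. Change is the only score type named anywhere in the documents, so that difference would most naturally be one of change scores. A change score uses baseline by subtraction, which fixes the slope at 1. A model with the baseline score as a covariate estimates the slope instead and usually gives a narrower interval. The baseline scores for all three scales are already in the data set, so the precision is available at almost no cost. With few randomised units, a chance difference between arms at baseline is also likely enough to plan for.

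**Working it through.** **Inputs from the documents.** Section 4.13 gives 60 participants, 6-8 clusters and 7-10 per cluster. That figure reproduces: 60/8 = 7.5 and 60/6 = 10. No effect size, SD, power or ICC is stated, so there is no other figure to reproduce.

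**Assumptions.** r is the baseline to follow-up correlation. k is follow-up SD divided by baseline SD. The baseline SD is set to 1 and the arms are equal in size. Illustrative numbers with a week-4 score are 60 (all) and 36. None of these, apart from the 60, comes from the documents.

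**Variance per patient.**
- Change score: 1 + k² − 2rk
- Adjusted for baseline: k²(1 − r²)
- The difference between the two is (1 − rk)², so the proportionate cut is (1 − rk)² / (1 + k² − 2rk)

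The cut is never negative before the cost of estimating the slope, and it is zero when rk = 1. Cut relative to change scores, ignoring clustering:

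| r | k = 0.8 | k = 1.0 | k = 1.2 | k = 1.3 |
|---|---|---|---|---|
| 0.5 | 42.9% | 25.0% | 12.9% | 8.8% |
| 0.7 | 37.2% | 15.0% | 3.4% | 0.9% |
| 0.9 | 39.2% | 5.0% | 2.3% | 8.3% |

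**Cost of the slope.** The variance is multiplied by (N − 3)/(N − 4): 57/56 = 1.018 with 60 patients and 33/32 = 1.031 with 36.
- Net cut at k = 1 with 60 patients: 1 − 0.75 × 1.018 = 23.7% (r = 0.5); likewise 13.5% (r = 0.7) and 3.3% (r = 0.9).
- Net cut at k = 1 with 36 patients: 22.7%, 12.3% and 2.0%.
- At rk = 1 (for example r = 0.7, k about 1.43) only the cost remains: a net loss of 1.8% with 60 and 3.1% with 36.

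**95% CI half-width, k = 1, follow-up SD units, clustering ignored.**

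| r | 60: change | 60: adjusted | 36: change | 36: adjusted |
|---|---|---|---|---|
| 0.5 | 0.517 | 0.452 | 0.677 | 0.596 |
| 0.7 | 0.400 | 0.373 | 0.525 | 0.492 |
| 0.9 | 0.231 | 0.227 | 0.303 | 0.300 |

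These widths are too narrow for a cluster trial. With an assumed ICC of 0.05 and t on 4-6 degrees of freedom, the change-score half-width at r = 0.7 with 60 patients is 0.56 (8 clusters) to 0.67 (6 clusters), against 0.40 above. The adjusted figures, before the slope cost, are 0.52 and 0.62.

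**Chance imbalance at baseline.** With m patients per cluster, SE = √[(2/30)(1 + (m − 1) × ICC)]. For ICC 0.05-0.10 this is 0.297-0.332 SD with m = 7.5 and 0.311-0.356 SD with m = 10. The probability of an imbalance above 0.3 SD is then 31-40%; with ICC 0 it is about 25%. An imbalance of 0.3 SD shifts a change-score difference by (r − 1) × 0.3, that is −0.15 at r = 0.5 and −0.09 at r = 0.7 (k = 1). This is the same variance seen conditionally, not a further loss.

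**The case against.** The strongest reply is that this is a descriptive pilot with feasibility as its primary objective and no formal test, and that 4.16 already promises the estimate. Much of that stands, and it rules out several stronger readings.

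- A reader might infer from the synopsis that no between-arm comparison is planned, or that the two sections conflict. Section 4.16 does plan differences and effect sizes with CIs for these three scales. The two statements are compatible, since both can be reported; they need aligning.
- A reader might infer that the unadjusted estimate is invalid or that an error rate is affected. Nothing supports that: a difference in change scores under randomisation is a legitimate estimate, and no test or power is claimed.
- A reader might set adjustment against raw follow-up scores and claim much larger savings. No passage states a raw-score analysis, so change scores are the fair comparator.
- A reader might infer that Phase III would be sized on the wrong SD. The pilot data would yield both the SD of change and the residual SD whichever contrast is listed, so that is conjecture.
- A reader might say that the yes/no items also cannot be analysed as the synopsis asks. They allow a within-group change in proportion. Only mRS, EQ-5D and the discharge items lack a baseline.

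It is also fair that clustering may move the interval more than baseline adjustment does, and that the gain over change scores can vanish. Neither is a reason to leave the model unstated when a named objective depends on the estimate.

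**Conclusion.** The point holds as a matter of alignment and precision. The synopsis row cannot by itself meet the effect-size objective and asks for change on measures that have no baseline. Section 4.16 plans the contrast without a model, and no passage uses the collected baseline scores as covariates.

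The gain from adjustment over change scores runs from sizeable to nil. At k = 1 with 60 patients it is about 24% of variance at r = 0.5 and about 3% at r = 0.9; near rk = 1 it becomes a net loss of about 2%, or 3% with 36 patients. All of this rests on assumed r and k and on figures that ignore clustering. The absolute half-widths should not be read as forecasts. Severity is minor to moderate.

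**What to change.** In both the synopsis and 4.16:

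- State the between-group difference (ILA minus standard care) with 95% CI for mRMI at 4 weeks, and for Fugl Meyer and SwePASS at the same time point, from a model with that scale's baseline score as a covariate. Use the same model that handles clustering; how clustering is handled is a separate decision, but the two should be specified together.
- Report the same contrast at 3 months.
- Beside each estimate, give the residual SD, the SD of change and the number of patients contributing.
- Label week 2, week 6 and discharge results as descriptive, because in-hospital measures run only up to discharge and later occasions may cover only patients still in hospital. Note the same limit on the number contributing at week 4; baseline adjustment need not correct for it.
- Keep within-group change as description, limited to measures that have a baseline. Report mRS, EQ-5D and discharge status as observed.

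The cost is wording in two places and one model degree of freedom, about 2% of variance with 60 patients and 3% with 36. No new data or visits are needed.
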